#### **11.4.6 Exploratory Analysis**

- Frequencies of actionable genotypes that guide drug/dose selection or modification will be summarized and described alongside types of mutations/phenotypes for each of the test genotypes.
- New medications prescribed and medication/dose adjustments based on PGx results will be summarized and described by frequencies of specific medication or medication classes prescribed and types of medication dose/adjustments, respectively.
- Drug/gene interactions present on the Baseline and the Final study visit will be grouped, summarized, and described qualitatively. Additionally, summary statistics of the numbers of interactions will be calculated.
- Calculate the following:
  - The proportion and 95% CI (using the Clopper-Pearson method) of PGx best practice advisory alerts that fire in Epic across all prescriptions across participants enrolled after the transition to Epic.

- The proportion and 95% CI (using the Clopper-Pearson method) of PGx best practice advisory alerts that fire in Epic across all new prescriptions within each participant enrolled after the transition to Epic.
- The proportion and 95% CI (using the Clopper-Pearson method) of actions taken from PGx best practice advisory alerts in Epic among all alerts fired across study participants enrolled after the transition to Epic.

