shown better clinical response with PGx-guided antidepressant selection [52-54] and tools have been developed to assist with PGx-based antidepressant prescribing [55,56].

PGx tests are now commercially available; however, due to their novelty, healthcare payors are reluctant to reimburse preemptive PGx screening and mandate further proof-of-concept and efficacy trials before coverage. Nonetheless, preemptive PGx testing increases the value proposition and prior studies suggest improved medication adherence and cost savings with PGx [57,58]. Further, many of the genes discussed earlier can affect non-oncology or non-supportive oncology medications that may be prescribed by other providers within the same health system (e.g., clopidogrel and CYP2C19). PGx results may be informative for management of other medications. Despite widespread availability of PGx tests and declining diagnostic costs, there is little data on the practicality of using PGx to improve supportive cancer care.

The Edmonton Symptom Assessment Scale (ESAS) (Appendix A) is a validated 10-item questionnaire assessing self-reported perceptions of pain, fatigue/energy, nausea, depression, anxiety, drowsiness, appetite, wellbeing, and shortness of breath. Each item is ranked from 0 to 10, with 10 representing the worst symptom. ESAS is routinely performed during all palliative medicine clinic visits. ESAS can be used to identify cancer patients presenting to palliative medicine with uncontrolled symptoms and can also be used to track symptom improvement or progression over time.

In a prior analysis we identified 46% of cancer patients at Levine Cancer Institute were prescribed a supportive care medication within 90 days of intake to the cancer hospital, mainly for pain (69%) and/or nausea (46%). Of these, 86% received at least one supportive care medication with PGx evidence and 84% received a CYP2D6-metabolized drug. Based on reported CYP2D6 allele frequencies conferring altered metabolism, 650 (20%) were expected to have altered drug response, suggesting preemptive PGx testing may have broad applicability in this population. PGx testing in this high-risk population may improve medication management and symptom control.

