### 2.1.3 Exploratory Objectives

- Determine the types & frequencies of actionable genotypes that result in drug/dose selection or modification(s) and those that do not result in drug/dose selection or modification(s).
- Describe the types of new medications prescribed (using medications of interest list; [Appendix D](#)) or medication/dose adjustments based on the PGx results.
- Determine the type & frequency of drug/gene interactions present at the Baseline and the Final study visit using CPIC guidelines and FDA's pharmacogenomics table.
- Summarize PGx best practice advisory alerts among participants enrolled after the transition to Epic to describe the proportion of participants that had a BPA fire in the EMR, the number and type of BPAs per participant, and any actions taken from the BPA.

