### 2.2.3 Exploratory Endpoints

- Binary variables will be recorded for each subject, indicating the presence or absence of an actionable genotype for each of the tested genotypes.
- Discrete variables will be recorded for each subject indicating the new medications prescribed or medication/dose adjustments made using the PGx results.
- Discrete variables will be recorded for each subject indicating the drug/gene interactions present at the Baseline and at the Final study visit. A count variable indicating the number of interactions will also be recorded.
- PGx best practice advisory (BPA) alerts: BPA alerts are fired within Epic when there is presence of a drug-gene interaction at the time of medication order entry. The following will be determined for study participants enrolled after the transition to Epic: a binary variable indicating the presence of a BPA in their EMR and a count variable indicating the total number of BPAs in their EMR.

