### 5.1.1 Schedule of Clinic Assessments

Every visit can occur during a clinic visit (in-person or utilizing virtual care) or over the phone. A subject can be assessed by a trained and delegated Palliative care provider, PharmD, study coordinator, or RN:

- Baseline (day 0) study visit should be no earlier than 2 weeks and no later than 8 weeks from the first ESAS completion.
- A total of 3 subsequent study visits and the Final visit will occur every 4 weeks ( $\pm$  1 weeks) after the Baseline visit. Additionally, non-protocol-directed visits may occur on an as-needed basis (e.g., an emergency due to uncontrolled symptoms).

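### The interval for alerts per prescription (section 11.4.6) treats prescriptions from one participant as independent, so it tends to be too narrow by an unknown amount

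*Combined protocol and SAP*

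**What the plan says.** Section 11.4.6 lists three alert proportions for participants enrolled after the move to Epic, each with a 95% Clopper-Pearson interval.

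- The first is the proportion of "PGx best practice advisory alerts that fire in Epic across all prescriptions across participants enrolled after the transition to Epic". The unit is the prescription, pooled over people.
- The second is the alert proportion "across all new prescriptions within each participant enrolled after the transition to Epic".
- The third is the proportion of "actions taken from PGx best practice advisory alerts in Epic among all alerts fired across study participants". The unit is the alert, again pooled over people.

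On what sets off an alert, section 2.2.3 says: "BPA alerts are fired within Epic when there is presence of a drug-gene interaction at the time of medication order entry". It defines "a binary variable indicating the presence of a BPA in their EMR" and a count of alerts per participant. The matching objective in section 2.1.3 is "to describe the proportion of participants that had a BPA fire in the EMR". Section 11.4.6 does not plainly list that participant-level proportion.

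Nothing in section 11.4.6 allows for several prescriptions or alerts from one person. The random subject effect in section 11.4.5 belongs only to the symptom-score models.

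**The concern.** A Clopper-Pearson interval has its stated coverage when the trials are independent with a common probability. Prescriptions from one participant share one germline genotype. Someone with altered CYP2D6 metabolism may trigger alerts on several orders, and someone without an actionable genotype on none. Table 1 in section 1.1 lists 17 drugs or drug classes under CYP2D6, so one gene can bear on several of a person's orders. In the site's earlier analysis of patients given a supportive care medication, "86% received at least one supportive care medication with PGx evidence and 84% received a CYP2D6-metabolized drug".

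If outcomes are positively correlated within a person, the pooled data carry less information than the prescription count suggests, and the reported interval claims too much precision. Only the width of an exploratory interval is at stake. The point estimates stand, and no test or decision rests on them.

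**Working it through.** **The plan's own precision figure.** Section 11.2 states a width of at most 25% with 65 evaluable subjects. The maximum Clopper-Pearson width at n = 65 is 25.3%, so the figure reproduces to rounding. It concerns the primary endpoint, with one observation per subject, and clustering does not touch it. No precision is stated for the alert proportions.

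**Inputs.** The documents give the interval, the 95% level and the pooled unit. They do not give the number of post-Epic participants (K), prescriptions per participant (m), alert rate (p) or ICC. Assumed ranges: K = 20 or 40, m = 3 or 6, p = 0.10, 0.25 or 0.40, ICC = 0 to 0.3.

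**Step 1: variance inflation.** The design effect is 1 + (m - 1) × ICC.

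- m = 3, ICC 0.1: 1 + 2 × 0.1 = 1.2; width should grow by √1.2 = 1.10.
- m = 6, ICC 0.1: 1 + 5 × 0.1 = 1.5; √1.5 = 1.22.
- m = 6, ICC 0.3: 1 + 5 × 0.3 = 2.5; √2.5 = 1.58.

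Example: 40 alerts in 200 prescriptions (40 participants, 5 each). The pooled interval is 14.7% to 26.2%, 11.5 points wide. With ICC 0.10 the design effect is 1 + 4 × 0.10 = 1.4, the effective n is 200/1.4 = 142.9, and the interval is 13.8% to 27.5% (13.7 points). With ICC 0.30 these become 2.2, 90.9 and 12.3% to 29.7% (17.4 points).

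**Step 2: coverage of the planned interval.** Each participant's alert count is beta-binomial with parameters p(1/ICC - 1) and (1 - p)(1/ICC - 1). The K counts are convolved exactly. Coverage is the total probability of the sums whose Clopper-Pearson limits contain p. Every participant has the same m.

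| p | m | ICC | K = 20 | K = 40 |
|---|---|---|---|---|
| 0.25 | 3 | 0 | 96.3% | 96.5% |
| 0.25 | 3 | 0.05 | 95.4% | 95.6% |
| 0.25 | 3 | 0.1 | 94.3% | 94.6% |
| 0.25 | 6 | 0 | 96.5% | 95.6% |
| 0.25 | 6 | 0.05 | 94.1% | 92.9% |
| 0.25 | 6 | 0.1 | 91.5% | 90.0% |
| 0.25 | 6 | 0.3 | 81.5% | 79.7% |
| 0.10 | 3 | 0.1 | 95.5% | 95.0% |
| 0.10 | 6 | 0.1 | 92.0% | 90.7% |
| 0.10 | 6 | 0.3 | 82.2% | 80.7% |
| 0.40 | 3 | 0.1 | 94.5% | 93.8% |
| 0.40 | 6 | 0.1 | 90.5% | 90.5% |
| 0.40 | 6 | 0.3 | 80.3% | 80.3% |

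With few prescriptions and a small ICC, the built-in conservatism of Clopper-Pearson absorbs the loss.

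**Step 3: the third proportion (alerts acted on).** Assumed: 8 to 20 participants with alerts, action rate 30% to 50%. Coverage is 95-99% with 2 alerts each and ICC 0.05-0.1, 92-94% with 5 and ICC 0.1, and 83-86% with 5 and ICC 0.3.

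**Step 4: candidate replacements for the first proportion** (20,000 simulated data sets per setting; equal and varying numbers per participant).

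- Logit-scale interval with a jackknife over participants and t limits: coverage about 95-96% at p = 0.25 and 94-98% at p = 0.10. Mean width is 1.03 to 1.72 times the pooled interval.
- Linear-scale clustered interval with t limits, at p = 0.10, m = 3, ICC 0.05 and equal numbers: coverage 93.7% (K = 20) and 92.2% (K = 40). The pooled Clopper-Pearson interval covers 96.3% and 95.9% there, so this replacement would do worse than the plan.

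**The case against.** The strongest reply is that the correlation may be small. The 84% counts patients with a CYP2D6 drug and does not show several such orders per patient. The same paragraph expects only 20% to have an altered response. Other drugs involve other genes, and some Appendix D drugs, such as gabapentin, are not in Table 1. With 3 prescriptions each and ICC 0.05-0.1, the planned interval has little or no error. This stands: the direction of the error is expected, but its size cannot be fixed from the documents. The analysis is also exploratory and meant to describe, which caps the severity.

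Two stronger readings are tempting and are not supported.

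- A reader might infer that coverage falls to 72-87%. That range assumes 3 distinct drugs, each ordered two or three times, with every repeat order counted and firing identically. The visit schedule ("A total of 3 subsequent study visits and the Final visit will occur every 4 weeks") implies about 4 × 4 = 16 weeks from Baseline to the Final visit, so repeat orders are possible. The documents do not say whether repeats count in the first proportion or fire again, and they set no observation window for alerts.
- A reader might infer that the interval for alerts acted on is certainly too narrow as well. The pooling is the same, but the documents describe no mechanism by which actions would correlate within a participant.

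The wording of the second proportion is a separate query. Read literally it is a rate for each person, with no pooling across people, so it does not carry this point.

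**Conclusion.** The point holds for the first proportion: the interval assumes independence where the documents' own description of alerts implies positive correlation within participants, so it tends to be too narrow. The loss runs from none to roughly 15 points of coverage (95% nominal against about 80%) over the assumed range, which rests on 20 to 40 participants, 3 or 6 prescriptions each, alert rates of 10% to 40% and ICC up to 0.3. None of these inputs comes from the documents. For the third proportion the concern applies only if actions cluster within participants. The severity is minor: the alert point estimates and the primary and secondary analyses are unaffected.

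**What to change.** **First proportion.** Replace the pooled Clopper-Pearson interval with one named clustered interval. Compute the pooled proportion P and its jackknife standard error SE, leaving out one participant at a time. Carry SE to the logit scale by the delta method, SE / (P(1 - P)). Take logit(P) ± t(K - 1) × that value and transform back. The plan should say that the jackknife is applied to the proportion and not to the logit itself. It should not allow a linear-scale clustered interval, which under-covers at low alert rates. When the clustered standard error is zero, give P without an interval; this happened in about 0.5% of samples or fewer in the settings checked.

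**Third proportion.** Use the same interval, or report the proportion descriptively when few participants contribute, with the threshold set in advance.

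**Participant-level proportion.** List the proportion of post-Epic participants with at least one alert in section 11.4.6, with a Clopper-Pearson interval. That is valid with one observation per participant; 10 of 20 gives 27% to 73%.

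**Wording, while editing.** State what the second proportion means and whether the first counts repeat orders.

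**Cost.** SAP wording and a few lines of code, with no change to design, sample size or data collection. The first interval becomes about 1.03 to 1.72 times as wide. The third may often have no interval when participants are few and actions rare: about 24-26% of samples with 8 participants, about 2 alerts each, action rate 10% and ICC 0.3.

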## **12. STUDY COMPLETION OR TERMINATION**

### **12.1 Completion**

The study will be considered complete when one or more of the following conditions is met:

- All subjects have withdrawn from the study
- All subjects have discontinued from the study
- The IRB, LCI DSMC, or Sponsor-Investigator discontinues the study because of safety considerations
- The Sponsor-Investigator defines an administrative or clinical cutoff date

### **12.2 Termination**

The study will be terminated when one or more of the following conditions occur:

- If risk-benefit ratio becomes unacceptable owing to, for example,
  - Safety findings from this study (e.g., UAPs)
  - Results of parallel clinical studies
  - If the study conduct (e.g., recruitment rate, drop-out rate, data quality, protocol compliance) does not suggest a proper completion of the trial within a reasonable time frame
- The Sponsor-Investigator has decided to close the trial at any site and at any time

For any of the above closures, the following applies:

- Closures should occur only after consultation between involved parties.
- All affected institutions must be informed as applicable according to local law.
- In case of a partial study closure, ongoing subjects, including those in follow-up, must be taken care of in an ethical manner.

## **13. STUDY MANAGEMENT**

### **13.1 IRB Approval**

The final study protocol and the final version of the informed consent form(s) must be approved in writing by the Sponsor IRB.

The Sponsor-Investigator is responsible for informing the Sponsor IRB of any amendment to the protocol in accordance with local requirements. The protocol must be re-approved by the IRB annually, as local regulations require.

### **13.2 Informed Consent**

Before recruitment and enrollment onto this study, the potential subject will be given a full explanation of the study and will be given the opportunity to review the consent form. Prior to a subject's participation in the trial, the written informed consent form should be signed and personally dated by the subject and by the person who conducted the informed consent discussion.

### **13.3 Protocol Adherence**

Except for an emergency situation in which proper care for the protection, safety and well-being of the study subject requires alternative treatment, the study shall be conducted exactly as described in the approved protocol.

### **13.4 Changes to the Protocol and/or Informed Consent**

#### **13.4.1 Amendments to the Protocol**

If it is necessary for the study protocol to be amended and/or the informed consent revised, the amendment or a new version of the study protocol (amended protocol) and/or the revised informed consent must be approved by the Sponsor-Investigator and the Sponsor IRB.

### **13.5 Protocol Deviations**

If a deviation occurs, the event should be reported to the Sponsor-Investigator promptly. Any IRB reportable event that occurs must be reported to the IRB per institutional policies and reported to the Sponsor-Investigator as soon as possible.

**NOTE:** Protocol deviations that, in the Investigator's judgment, potentially caused harm to participants or others or indicates that the participants or others are at an increased risk of harm, or has adversely impacted data integrity will be reported promptly to the IRB per IRB reporting requirements.

### **13.6 Retention of Records**

Essential documentation (e.g., informed consents), including all IRB correspondence, will be retained for at least 2 years after the investigation is completed. Documentation will be readily available upon request.

### **13.7 Ethical and Legal Conduct of the Study**

The procedures set out in this protocol, pertaining to the conduct, evaluation, and documentation of this study, are designed to ensure that the Investigator abide by GCP guidelines. The study will also be carried out in full conformity with Regulations for the Protection of Human Subjects

of Research codified in 45 CFR Part 46, 21 CFR Part 50, 21 CFR Part 56, and/or the ICH E6 and in keeping with applicable local law(s) and regulation(s).

Documented approval from appropriate agencies (e.g., IRB) will be obtained for all participating centers before the start of the study, according to GCP, local laws, regulations and organizations.

Strict adherence to all specifications laid down in this protocol is required for all aspects of study conduct; the investigators may not modify or alter the procedures described in this protocol.

The Sponsor-Investigator is responsible for the conduct of the trial at the sites in accordance with Title 21 of the CFR and/or the Declaration of Helsinki. The Sponsor-Investigator is responsible for overseeing all study subjects. The Sponsor-Investigator must assure that all study site personnel, including sub-investigators and other study staff members, adhere to the study protocol and all applicable regulations and guidelines regarding clinical trials both during and after study completion.

The Sponsor-Investigator will be responsible for assuring that all the required data will be collected and properly documented.

### **13.8 Confidentiality of Records**

All records identifying the subject will be kept confidential and, to the extent permitted by the applicable laws and/or regulations, will not be made publicly available.

## 15. APPENDIX A. EDMONTON SYMPTOM ASSESSMENT SCALE

**Please circle the number that best describes:**

No pain	0	1	2	3	4	5	6	7	8	9	10	Worst possible pain
Not tired	0	1	2	3	4	5	6	7	8	9	10	Worst possible tiredness
Not nauseated	0	1	2	3	4	5	6	7	8	9	10	Worst possible nausea
Not depressed	0	1	2	3	4	5	6	7	8	9	10	Worst possible depression
Not anxious	0	1	2	3	4	5	6	7	8	9	10	Worst possible anxiety
Not drowsy	0	1	2	3	4	5	6	7	8	9	10	Worst possible drowsiness
Best appetite	0	1	2	3	4	5	6	7	8	9	10	Worst possible appetite
Best feeling of wellbeing	0	1	2	3	4	5	6	7	8	9	10	Worst possible feeling of wellbeing
No shortness of breath	0	1	2	3	4	5	6	7	8	9	10	Worst possible shortness of breath
Other problem	0	1	2	3	4	5	6	7	8	9	10	

## 16. APPENDIX B. PATIENT HEALTH QUESTIONNAIRE (PHQ) 9

Protocol: LCI-SUPP-NOS-PGx-001 Date \_\_\_\_\_

Study Sequence ID \_\_\_\_\_

Initials \_\_\_\_\_

DOB \_\_\_\_\_

### PATIENT HEALTH QUESTIONNAIRE-9 (PHQ-9)

Over the last 2 weeks, how often have you been bothered by any of the following problems?  
(Use "✓" to indicate your answer)

	Not at all	Several days	More than half the days	Nearly every day
1. Little interest or pleasure in doing things	0	1	2	3
2. Feeling down, depressed, or hopeless	0	1	2	3
3. Trouble falling or staying asleep, or sleeping too much	0	1	2	3
4. Feeling tired or having little energy	0	1	2	3
5. Poor appetite or overeating	0	1	2	3
6. Feeling bad about yourself — or that you are a failure or have let yourself or your family down	0	1	2	3
7. Trouble concentrating on things, such as reading the newspaper or watching television	0	1	2	3
8. Moving or speaking so slowly that other people could have noticed? Or the opposite — being so fidgety or restless that you have been moving around a lot more than usual	0	1	2	3
9. Thoughts that you would be better off dead or of hurting yourself in some way	0	1	2	3

For office coding 0 + \_\_\_\_\_ + \_\_\_\_\_ + \_\_\_\_\_  
=Total Score: \_\_\_\_\_

If you checked off any problems, how difficult have these problems made it for you to do your work, take care of things at home, or get along with other people?

Not difficult at all	Somewhat difficult	Very difficult	Extremely difficult
			

## 17. APPENDIX C. PGX PATIENT SURVEY

Protocol: LCI-SUPP-NOS-PGx-001

### PGx Survey

--

Date: \_\_\_\_\_

Subject identifier

**Pharmacogenomics** is the study of how one's genetic makeup (i.e. their DNA) influences response to medications. Pharmacogenetic testing may identify changes in genes that control how one processes (e.g. metabolizes) medications in their body. These results may be useful in identifying whether someone might respond differently to a specific medication.

1. What is your educational level?				
Less than high school degree		High school degree or equivalent		Some college but no degree
Associate degree	Bachelor's degree	Graduate degree	Prefer not to answer	
2. What is your annual household income?				
\$0 - \$15,000		\$15,001 - \$30,000		\$30,001 - \$45,000
\$45,001 - \$60,000		\$60,001 - \$75,000		\$75,001 - \$90,000
		More than \$90,000		Prefer not to answer
3. Had you heard about pharmacogenetic testing prior to participating in this study?				
Yes		No		
4. Did you understand the purpose of pharmacogenetic testing before this study?				
Yes		No		Never heard of it
5. Did you understand the purpose of pharmacogenetic testing after enrolling on this study?				
Yes		Somewhat		No
6. How comfortable are you with understanding your pharmacogenetic test results?				
Very comfortable		Somewhat comfortable		Not comfortable
7. Do you think your results were or will be useful for managing your medications?				
Very likely		Somewhat likely		Not likely
8. How satisfied are you with communication of your test results by the clinic staff?				
Very satisfied		Somewhat satisfied		Not satisfied
9. Overall, are you satisfied with the care you received as part of this study?				
Very satisfied		Somewhat satisfied		Not satisfied
10. Would you recommend pharmacogenetic testing to a family member/friend?				
Very likely		Somewhat likely		Not likely
11. After learning about pharmacogenetics, what would you be willing to pay for testing?				
\$200		\$300		\$400
		\$500		I would not pay for pharmacogenetic testing

Research designee name: \_\_\_\_\_

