### 2.2.2 Secondary Endpoints

- A count variable will be recorded for each subject undergoing PGx testing indicating the total number of drug/dose selections or modifications received across all study visits where PGx results were available.
- Pain scores assessed by the ESAS and depression scores using PHQ9 will be recorded for each subject at the Baseline and all the visits.
- Health care resource utilization (HCRU) and costs will be estimated based on the number of inpatient, emergency department, outpatient, and pharmacy encounters, among others, occurring one year prior to and during the study period.
- Discrete variables will be recorded to indicate subject survey responses.

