## **11.2 Sample Size and Accrual**

Enrollment to the study will continue until 65 evaluable subjects have been identified ([Section 11.3](#)).

We anticipate enrolling 80 eligible subjects, of which we estimate 65 will be evaluable (defined in [11.3](#)). With this sample size, the width of the 95% Clopper-Pearson confidence interval will be  $\leq 25\%$ , regardless of the observed DDSM rate.

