## **11.3 Analysis Populations**

Analyses of the primary objectives and secondary objectives concerning counts of PGx-guided drug/dose selections or modifications based on their test results will be conducted on the evaluable population, defined as the population of enrolled subjects with confirmed malignancy (per provider documentation) and completing at least one study visit where PGx results are available (including the baseline visit).

Analyses of secondary objectives concerning the impact of PGx on pain and depression scores will be conducted on the primary evaluable population with valid pain and/or depression scores for at least one post-Baseline Study visit.

Analyses of secondary objectives concerning health care utilizations, costs, and subject survey responses and all exploratory objectives will be conducted on all enrolled subjects.

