Health care utilization (e.g., instances of participant presenting at an emergency department, admitted as an inpatient, any outpatient encounter, or medication prescription) and reason for encounter will be assessed during the study period (starting on the Baseline to the Final study visit) for those undergoing PGx testing. HCRU in year prior to start of study enrollment will be collected for patients from institutional enterprise data warehouse (EDW) via raw billing and medical record data. Insurance status and/or type at each encounter will also be collected. An encounter resulting from another (e.g., ED presentation leading to IP) will be counted separately. Any ED encounter lasting longer than 24 hours will be considered an IP encounter. Diagnosis and procedure codes and priority sequence numbers will be collected from the EDW at least 6 months following study closure to allow for final bills to accrue for HCRU encounters, for those that underwent PGx testing and matched controls. Diagnosis and procedure codes used in billing for each encounter will be used to estimate institutional costs or reimbursement and/or to publicly available sources (e.g., CMS fee schedule) and to obtain patient's historical prescription drugs. Endpoints will be summarized by encounter-level and patient-level data files for frequency of HCRU and descriptive analysis of associated cost. Once data files have been constructed, data will be fit to appropriate statistical analyses and multivariate regression will be employed to interrogate the relationship between costs, resource utilization PGx results, sociodemographic, and clinical patient characteristics. Sensitivity and scenario analyses will be conducted to assess the robustness of model estimates.

Subject responses to survey tool administered at the Final visit (or sooner if withdrawn) will be summarized and described. Regression models may be estimated to describe the association of response and responder characteristic, both univariately and multivariately, adjusted for relevant baseline characteristics.

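### Survey item 11 has no answer for amounts between zero and $200 or above $500, so the share unwilling to pay may be overstated

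*Combined protocol and SAP*

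**What the plan says.** Appendix C, item 11, asks "After learning about pharmacogenetics, what would you be willing to pay for testing". It has five answers: $200, $300, $400, $500 and "I would not pay for pharmacogenetic testing". It offers no amount below $200, no class above $500, no free-text amount and no way to decline. By contrast, item 2 of the same survey (household income) runs without gaps from $0 to an open-ended top class and lets the respondent decline.

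Section 2.2.2 makes survey answers a secondary endpoint: "Discrete variables will be recorded to indicate subject survey responses". Section 11.4.5 says: "Subject responses to survey tool administered at the Final visit (or sooner if withdrawn) will be summarized and described". It adds an optional step: "Regression models may be estimated to describe the association of response and responder characteristic". Section 11.3 sets the population: analyses of "subject survey responses and all exploratory objectives will be conducted on all enrolled subjects". Section 11.2 gives the expected size: "We anticipate enrolling 80 eligible subjects, of which we estimate 65 will be evaluable". No section says how an amount below $200 is to be coded.

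**The concern.** The refusal option is worded absolutely. It says the respondent would not pay, not that the respondent would not pay the lowest listed price. Someone who would pay $50 or $100 fits neither that statement nor any listed amount. A published percentage unwilling to pay could then mix people who would pay nothing with people who would pay something less than $200.

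The item could attract outside interest, because Section 1.1 gives payor reluctance to reimburse preemptive testing as part of the background. What is at stake is the meaning of one reported percentage and of its neighbouring $200 category.

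**Working it through.** The plan gives no figure for this item, so there is nothing to reproduce. The check reads the answer list for gaps and then follows each way an affected respondent could answer.

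**Inputs**
- Lowest and highest listed amounts: $200 and $500 (Appendix C, item 11).
- Survey population: all enrolled subjects, about 80 expected (Sections 11.3 and 11.2).
- *s*, the share who would pay $1-199: not in the documents; assumed 0% to 30%.
- *r*, the share who truly would pay nothing: not in the documents; 20% and 40% used as illustrations.
- *f*, the fraction of *s* who tick refusal: unknown, between 0 and 1.

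**If everyone answers the item**
- Observed refusal = *r* + *s* × *f*, so the overstatement is *s* × *f*.
- The rest, *s* × (1 − *f*), tick $200 and overstate that category.

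| *s* | Refusal overstated, *f* = 1 | Refusal overstated, *f* = 0.5 ($200 overstated equally) | $200 overstated, *f* = 0 |
|---|---|---|---|
| 0% | 0 points | 0 points | 0 points |
| 10% | 10 | 5 | 10 |
| 20% | 20 | 10 | 20 |
| 30% | 30 | 15 | 30 |

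With *f* = 1 and *r* = 20%, observed refusal is 30%, 40% or 50% for *s* = 10%, 20% or 30%. With *r* = 40% it is 50%, 60% or 70%.

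**If all affected respondents skip the item**
- Refusal among those who answer = *r* / (1 − *s*).
- *r* = 20%: 0.20/0.90 = 22.2%, 0.20/0.80 = 25.0%, 0.20/0.70 = 28.6%.
- *r* = 40%: 0.40/0.90 = 44.4%, 0.40/0.80 = 50.0%, 0.40/0.70 = 57.1%.
- The overstatement is *r* × *s* / (1 − *s*). Since *r* cannot exceed 1 − *s*, this is never more than *s*. It reaches *s* only in the extreme case where nobody would pay $200 or more.

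**Scale against sampling error**

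If all 80 answered and 16 refused (20%), the 95% Clopper-Pearson interval would be 11.9% to 30.4%. With *s* = 20% and *f* = 1, 32 of 80 (40%) would appear to refuse, with interval 29.2% to 51.6%, which excludes the assumed true 20%. With *s* = 10% and *f* = 1, 24 of 80 (30%) would appear to refuse, with interval 20.3% to 41.3%, which only just excludes it.

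**Top of the scale**

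A respondent who would pay more than $500 can only tick $500 or skip. Ticking $500 does not change the count of refusals, but the $500 category then cannot be told apart from larger amounts.

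**The case against.** The strongest reply is that the item is minor and the direction of error is not fixed. The plan states no willingness-to-pay objective and attaches no hypothesis, precision target or decision to item 11. It is one of eleven items in a survey meant to describe patients' views. This stands, and it keeps the point small.

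A reader might infer that every respondent willing to pay $1-199 is misclassified and that the refusal share is certainly biased. The documents do not support that. Someone who skips the item is missing, not misclassified. If all affected respondents round up to $200, the refusal share is unaffected and only the $200 share is wrong. If nobody falls in the gap, nothing is wrong.

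A reader might also infer that low amounts cluster at low income, so that an income analysis of this item must be wrong. Nothing in the documents says where low amounts fall. Section 11.4.5 says only that regression models may be fitted, and it names neither income nor item 11. Income is collected in the same survey, so such a model is possible, but it is not planned in the text.

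It is also fair to say that the 30-point figure is an assumed worst case, not an estimate, and that changing the wording during collection splits a small sample. None of this supplies an answer for the respondent who would pay less than $200.

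**Conclusion.** The gap is real: item 11 has no true answer for amounts of $1-199 or above $500, and no coding rule elsewhere repairs it. Overstatement of the refusal share is possible but not certain. Under an assumed affected share of 0% to 30%, it ranges from 0 to 30 percentage points. The upper end needs 30% of respondents in the gap and all of them ticking refusal. If they round up, the error moves to the $200 category. If they skip, it becomes missing data, generally with a smaller rise in refusal among those who answer. The true size cannot be found from the documents.

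This is a small, inexpensive improvement to one descriptive secondary item. It does not touch the primary endpoint, the sample size or the symptom analyses.

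**What to change.** For surveys not yet administered, add a *Less than $200* option to item 11, and a *More than $500* option to close the top of the scale. The second does not bear on the refusal share.

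For surveys already collected, report item 11 separately by survey version and describe the last option as *would not pay $200 or more*. That label correctly describes both true refusers and those who ticked refusal because their amount was too low. State beside it that respondents who rounded up to $200 or left the item blank cannot be recovered, and give the number of blanks.

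The cost is a survey wording amendment and, if collection has begun, two versions among about 80 enrolled subjects. If that split is judged not worthwhile, the reporting label alone needs no amendment and prevents the main misreading.
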